6.3.4 Clinical Safety Laboratory Assessments

6.3.4.1 Urine Pregnancy Test

For female subjects of childbearing potential who have been heterosexually active in their lifetime, a urine pregnancy test will be performed at screening and prior to any study vaccination (at the discretion of the investigator based on history taking).

6.3.4.2 SARS-CoV-2 Test

Given the ongoing pandemic, a SARS-CoV-2 test for active infection (an approved local test accepted by public health authorities and readily available) will be administered to subjects within 72 hours prior to vaccination (Day 1 for all subjects or Day 85 if in substudy). Should the subject have a positive SARS-CoV-2 test result, regardless of symptomatology, then vaccination will be temporarily held until the subject has a negative test result.

6.3.5 Adverse Events

6.3.5.1 Definitions of Adverse Events

The investigator is responsible for reporting all AEs that are observed or reported during the study, regardless of their relationship to study vaccination or their clinical significance.

An AE is defined as any untoward medical occurrence in a subject enrolled into this study regardless of its causal relationship to study vaccination. Subjects will be instructed to contact the investigator at any time after study vaccination if any symptoms develop.

6.3.5.1.1 Serious Adverse Events

An SAE is defined as any event that

- results in death
- is immediately life threatening
- requires inpatient hospitalization or prolongation of existing hospitalization
- results in persistent or significant disability/incapacity
- is a congenital anomaly/birth defect

Important medical events that may not result in death, be life threatening, or require hospitalization may be considered SAEs when, based upon appropriate medical judgment, they may jeopardize the subject or may require medical or surgical intervention to prevent one of the outcomes listed in this definition. Examples of such medical events include allergic bronchospasm requiring intensive treatment in an emergency room or at home, blood dyscrasias or convulsions that do not result in inpatient hospitalization, or the development of drug dependency or drug abuse.

At the discretion of the investigator, additional local laboratory or diagnostic assessments (including additional blood sampling) may be performed on any subject who experiences an SAE.

6.3.5.1.2 Local (Arm), Nasal/Respiratory, and General Systemic Reactogenicity

Reactogenicity events are common and known to occur following administration of vaccines, indicating a positive immune response is being mounted. Site-specific local (arm), nasal/respiratory, and general systemic reactogenicity events including start and stop dates/times will be recorded and a standard toxicity grade (refer to Section 13.2) will be applied to any reactogenicity event.

6.3.5.1.3 Medically Attended Adverse Events

A medically attended AE is defined as any unsolicited AE that leads to an unscheduled visit to a healthcare provider, or any grade 3 solicited reactogenicity event that leads to an unscheduled visit to a healthcare provider.

6.3.5.1.4 Adverse Events of Special Interest

If the COVID-19 pandemic remains ongoing in the region or if there are mass vaccinations using a COVID-19 vaccine during study conduct, any symptoms associated with COVID-19 infection or vaccination will be collected as an AESI on a unique COVID-19 eCRF through Day 169/EOS.

6.3.5.2 Assessing and Documenting Adverse Events

Safety will be assessed by the frequency and severity of:

1. All AESIs and SAEs occurring from the time of vaccination through Day 169/EOS.
2. All MAAEs occurring through 84 days following any vaccination.
3. Solicited reactogenicity events occurring from the time of any study vaccination for 7 consecutive days starting the day following study vaccination, including:
 - a. Nasal/respiratory reactions (runny/congested nose, sore/irritated throat, cough, sneeze, nasal or sinus pain/irritation, difficulty breathing/wheezing; if epistaxis occurs it should be listed as an AE);
 - b. Systemic reactions (fever, headache, fatigue/malaise, loss of appetite/anorexia, vomiting, diarrhoea, nausea, myalgia, acute allergic reaction/urticaria); and
 - c. Local reactions (pain/tenderness, redness, swelling [after IM injection only]).
4. Unsolicited AEs – all AEs regardless of causality, will be collected for 28 days after any vaccination. Between screening (signing of ICF) and Day 1, AEs will be collected if classified as serious or if considered related to study procedure or study involvement. Any event that results in vaccination delay (eg, temporary exclusions due to acute upper respiratory symptoms/illness or fever, or investigator determined medical condition) during screening or during study conduct will also be recorded as an AE. Should any reactogenicity event extend beyond 7 days following vaccination, it will be recorded as an AE with the same start date as the reactogenicity event and followed until considered resolved.

At every study visit, subjects will be asked a standard non-leading question to elicit any medically related changes in their well-being that would pertain to the AEs being collected at the time. They will also be asked if they have been hospitalized, had any accidents, used any new medications, received a vaccination or changed concomitant medication regimens (both prescription and OTC medications).

6.3.5.3 Reporting Adverse Events

Adverse events reported or observed during the study will be recorded on the AE page in the eCRF.

An AE is any unfavourable and unintended sign, symptom, or disease. The occurrence of an AE may come to the attention of study personnel during study visits and interviews of a study recipient presenting for medical care, or upon review by a study monitor. A single AE may have a constellation of signs/symptoms and the single most precise Medical Dictionary for Regulatory Activities (MedDRA) term should be utilized as the AE classification to avoid duplication of AEs.

Adverse events will be captured on the appropriate data collection form and eCRF. Information to be collected for unsolicited nonserious AEs includes event description, date of onset, licensed study physician's assessment of severity and relationship to study vaccination and alternate aetiology (if not related to study vaccination), date of resolution of the event, seriousness, and outcome. Adverse events occurring during the collection and reporting period will be documented appropriately regardless of relationship (as defined in Section 6.3.5.7).

Any medical condition that is present at the time that the subject is screened will be considered as baseline (recorded as medical history) and not reported as an AE; however, if the severity of any pre-existing medical condition increases, it will be recorded as an AE.

Adverse events must be graded for severity and assessed for relationship to study vaccination. Adverse events characterized as intermittent require documentation of onset and duration of each episode. The start and stop date of each reported AE will be recorded on the appropriate data collection form and eCRF.

Adverse events resulting from concurrent illnesses, reactions to concurrent illnesses, reactions to concurrent medications, or progression of disease states must also be reported. All AEs will be followed to adequate resolution. The MedDRA will be used to code all AEs.

6.3.5.4 Reporting Serious Adverse Events

Any AE that meets SAE criteria (Section 6.3.5.2) must be reported to the CRO immediately (ie, within 24 hours) after the time site personnel first learn about the event. The contact information to be used for SAE reporting will be provided to the CRO and the CRO will oversee the SAE reporting.

6.3.5.5 Suspected Unexpected Serious Adverse Reactions

The sponsor will promptly evaluate any new suspected unexpected serious adverse reactions (SUSARs) and expeditiously communicate possible new safety findings to investigators, institutional review boards or independent ethics committees, and applicable health authorities based on applicable legislation. Any SAE considered to be related to BPZE1 will be classified as a SUSAR.

To determine reporting requirements for single AE cases, the sponsor will assess the expectedness of these events using the most recent version of the IB or the package insert for Boostrix (BOOSTRIX 2020). A summary of the possible undesirable effects from Boostrix (Boostrix 2021) is provided in Section 1.3.1.3.

Reporting requirements will also be based on the investigator's assessment of causality and seriousness, with allowance for upgrading by the sponsor as needed.

6.3.5.6 Assessment of Severity

The severity, or intensity, of an AE refers to the extent to which an AE affects the subject's daily activities. The intensity of the AE will be rated as mild, moderate, or severe using the following criteria:

Mild: These events require minimal or no treatment and do not interfere with the subject's normal daily activity.

Moderate: These events result in a low level of inconvenience or concern with the therapeutic measures. Moderate events may cause some interference with normal functioning.

Severe: These events interrupt a subject's normal daily activity and may require systemic drug therapy or other treatment. Severe events are usually incapacitating.

Changes in the severity of an AE should be documented to allow an assessment of the duration of the event at each level of intensity to be performed. Adverse events characterized as intermittent require documentation of onset and duration of each episode.

6.3.5.7 Assessment of Causality

The investigator's assessment of an AE's relationship to study vaccination is part of the documentation process, but it is not a factor in determining what is or is not reported in the study. If there is any doubt as to whether a clinical observation is an AE, the event should be reported.

The relationship or association of the test article in causing or contributing to the AE will be characterized using the following classification and criteria:

Related: There is a reasonable possibility that the study vaccination caused the AE. Reasonable possibility means that there is evidence to suggest a causal relationship between the study vaccination and the AE.

Not Related: There is not a reasonable possibility that the study vaccination caused the event.

6.3.5.8 Follow-Up of Subjects Reporting Adverse Events

All AEs must be reported in detail on the appropriate page in the eCRF and followed to satisfactory resolution, until the investigator deems the event to be chronic or not clinically significant, or until the subject is considered to be stable. Adverse events will be collected, assessed, and followed through resolution, considered stable or when subject completes EOS and based on Section 6.3.5.4. Serious AEs will be collected, assessed, and followed through EOS or until satisfactory resolution or clinically stable.

Resolution of an AE/SAE is defined as the return to pre-treatment status or stabilization of the condition with the expectation that it will remain chronic.

If the investigator becomes aware of an acute illness and the investigator decides to bring the subject in for an evaluation to determine aetiology, then the investigator, at their own discretion, can determine the specific testing that should be performed (including additional blood sampling). Follow-up procedures, evaluations, and outcomes will be recorded on the appropriate data collection form.

6.4 Immunogenicity and Colonization Assessments

Immune measurements will be conducted on serum (IgG and IgA) and nasal mucosal secretion (S-IgA) samples for anti-pertussis antibodies of WCE, PT, FHA, and PRN as well as any additional anti-pertussis antibodies included in assay development. Serum bactericidal activity (or other functional assays identified) will be measured in a subset of subjects.

Cellular-mediated response to BPZE1 and Boostrix (Th1/Th17 vs Th2) will be assessed by ELISpot or flow cytometry at baseline and Day 8 (safety lead-in cohort) and Day 85 and Day 113 (subset of substudy subjects). Additional testing for antigens specific to *B. pertussis* may be performed at a later date as BPZE1 induces broader immunity more similar to natural infection induced immunity and does not contain the purified antigen levels of PT, FHA, and PRN found in Boostrix. Mid-turbinate/nasopharyngeal samples will be evaluated by real-time PCR or by *B. pertussis* culture for colonization of BPZE1.

Subjects will consent for the use of samples for further anti-pertussis antibody testing or other assay development as part of the standard consenting process. Aliquots of collected samples from this study may be retained for additional testing of biological responses (eg, antibodies, T-cell responses, microbiome) specific to future development of BPZE1 and ILiAD Biotechnologies' *B-Tech* program for a maximum of 15 years (starting from the date at which the last subject had the last study visit), unless local rules, regulations, or guidelines require different time frames or different procedures, and in accord with subject consent.

Procedures for the handling and processing of immunogenicity samples are provided in the laboratory manual or the site manual.

6.5 Vaccination Pause Rules

Further enrolment and study vaccinations will be halted (paused) for SMC review/recommendation if any of the following are reported:

- Any subject experiences ulceration, abscess, or necrosis in the nose that is considered related to study vaccination, through 28 days following study vaccination.
- Any subject experiences severe respiratory symptoms of laryngospasm, shortness of breath or wheezing (grade 3 or greater) within 3 days of study vaccination.
- Any subject experiences an SAE considered related to study vaccination from the time of the vaccination through the subject's last study visit.
- More than 12 subjects report a grade 3 fever within 7 days of study vaccination that is attributed to study vaccination when no other cause can be found (corresponding to an incidence rate of approximately 3% for Boostrix).

Grading scales for solicited reactogenicity events are included in Section 13.2.

If any of the vaccination pause rules are met following any subject receipt of study vaccination, then this study will not continue with the remaining enrolments or future study vaccinations without a review by the SMC and a recommendation from the SMC to proceed (with or without alteration of protocol). Vaccination windows will be adjusted for any such pause to allow subjects to remain within the expected schedule of events. All events that classify for vaccination pause rules will be entered as AEs.

The sponsor retains the authority to suspend additional enrolment and study interventions or administration of study vaccine during the entire study, as applicable.

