Infections and infestations	Uncommon	Upper respiratory tract infection	Upper respiratory tract infection, pharyngitis
Blood and lymphatic system disorders	Uncommon		Lymphadenopathy
Metabolism and nutrition disorders	Common	Anorexia	
Psychiatric disorders	Very common	Irritability	
Nervous system disorders	Very common	Somnolence	Headache
	Common	Headache	Dizziness
	Uncommon	Disturbance in attention	Syncope
Eye disorders	Uncommon	Conjunctivitis	
Respiratory, thoracic and mediastinal disorders	Uncommon		Cough
Gastrointestinal disorders	Common	Diarrhoea, vomiting, gastrointestinal disorders	Nausea, gastrointestinal disorders
	Uncommon		Diarrhoea, vomiting
Skin and Subcutaneous tissue disorders	Uncommon	Rash	Hyperhidrosis, pruritis, rash
Musculoskeletal and connective tissue disorders	Uncommon		Arthralgia, myalgia, joint stiffness, musculoskeletal stiffness
General Disorders and administration site conditions	Very Common	Injection site reactions (such as redness and/or swelling), injection site pain, fatigue	Injection site reactions (such as redness and/or swelling), malaise, fatigue, injection site pain
	Common	Pyrexia (fever $\geq 37.5^{\circ}\text{C}$ including fever $> 39.0^{\circ}\text{C}$), extensive swelling of vaccinated limb (sometimes involving the adjacent joint)	Pyrexia (fever $\geq 37.5^{\circ}\text{C}$), injection site reactions (such as injection site mass and injection site abscess sterile)
	Uncommon	Other injection site reactions (such as induration), pain	Pyrexia (fever $> 39.0^{\circ}\text{C}$), influenza like illness, pain

Reactogenicity After Repeat Dose

Data on 146 subjects suggest that there might be a small increase in local reactogenicity (pain, redness, swelling) with repeated vaccination according to a 0, 1, 6 months schedule in adults (> 40 years of age).

Data suggest that in subjects primed with DTP in childhood, a second booster dose might give an increase of local reactogenicity.

Post-Marketing Surveillance

Because these events were reported spontaneously, it is not possible to reliably estimate their frequency (Table 1-2).

Table 1-2 *Adverse Reactions Reported with Boostrix During Post-Marketing Surveillance*

System Organ Class	Frequency	Adverse Reactions
Immune system disorders	Unknown	Allergic reactions, including anaphylactic and anaphylactoid reactions

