3.1 Study Design

This is a multi-centre, randomized, observer-blinded, placebo- and active comparator-controlled trial with a 6-month safety follow-up after first study vaccination. After signing the informed consent form (ICF; or providing assent when necessary) and meeting all inclusion and none of the exclusion criteria, eligible subjects will receive an intranasal vaccination with either BPZE1 vaccine or formulation buffer (placebo) via the MAD and an intramuscular (IM) injection of either Tdap vaccine (i.e., Boostrix) or sterile normal saline (placebo) on Day 1. To maintain the blind, placebo vaccination via intranasal and IM routes, using formulation buffer and normal saline, respectively, will be included, and an unblinded team will manage vaccine logistics, preparation, and administration (when needed to maintain blinding) but will not be involved in study-related assessments or have subject contact for data collection after study vaccination.

Approximately 360 subjects will be enrolled and randomly assigned (1:1:1) to 1 of 3 treatment groups (refer to Table 3-1) to contribute to safety and efficacy assessments. Enrolment will be operationally managed at the study level to maintain a minimum number of subjects enrolled in 2 age groups: 6 to 10 years, inclusive; and 11 to 17 years, inclusive. It is estimated that a 10% dropout rate will occur, allowing for approximately 108 evaluable subjects per treatment group.

Table 3-1 Dosing Scheme

Treatment Group	n	Intranasal Vaccination ^a (Day 1)		IM Vaccination ^b (Day 1)	
		BPZE1	Placebo	Boostrix	Placebo
A	120	X	-	-	X
B	120	X	-	X	-
C	120	-	X	X	-

^a Intranasal application of ~0.4 mL per nostril (0.8 mL total volume delivered). Intranasal vaccination will occur prior to IM vaccination.

^b IM injection of 0.5 mL to the deltoid region.

All subjects will be monitored for at least 30 minutes after final study vaccination. On Day 1, intranasal vaccination will occur prior to IM vaccination with a minimum of 10 minutes (minimum of 30 minutes for subjects in the safety lead-in cohort of 11 to 17 year olds)

between intranasal and IM vaccinations. Immediate reactogenicity will be assessed at 30 minutes (+30 minutes) after the last study vaccination of the Day (ie, after IM vaccination on Day 1, after nasal vaccination on Day 85), prior to release from clinical observation.

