5.2 Treatments Administered

Subjects in Treatment Group A (N ~120) will receive an intranasal application of 10^9 CFU BPZE1, with approximately 0.4 mL per nostril (0.8 mL total volume delivered); and an IM injection of 0.5 mL placebo (sterile normal saline for injection) to the deltoid region on Day 1. Intranasal application of BPZE1 or placebo should precede IM injection of Boostrix or placebo by at least 10 minutes (minimum of 30 minutes for subjects in the safety lead-in cohort of 11 to 17 year olds). For the safety lead-in cohort, a minimum of 30 minutes must occur between intranasal and IM vaccinations on Day 1.

Subjects in Treatment Group B (N ~120) will receive an intranasal application of 10^9 CFU BPZE1, with approximately 0.4 mL per nostril (0.8 mL total volume delivered); and an IM injection of 0.5 mL Boostrix (aP vaccine, manufactured by GlaxoSmithKline) to the deltoid region on Day 1. Intranasal application of BPZE1 or placebo should precede IM injection of Boostrix or placebo by at least 10 minutes (minimum of 30 minutes for subjects in the safety lead-in cohort of 11 to 17 year olds).

Subjects in Treatment Group C (N ~120) will receive an intranasal application of lyophilized buffer reconstituted in sterile water, with approximately 0.4 mL per nostril (0.8 mL total volume delivered); and an IM injection of 0.5 mL Boostrix (aP vaccine, manufactured by GlaxoSmithKline) to the deltoid region on Day 1. Intranasal application of BPZE1 or placebo should precede IM injection of Boostrix or placebo by at least 10 minutes (minimum of 30 minutes for subjects in the safety lead-in cohort of 11 to 17 year olds).

All subjects participating in the optional substudy will receive a second intranasal application of 10^9 CFU BPZE1, with approximately 0.4 mL per nostril (0.8 mL total volume delivered) on Day 85.

All subjects will be monitored for study vaccination-related events for at least 30 minutes following the last vaccination (eg, 30 minutes following IM vaccination).

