Headache	Easily tolerated, causing no or minimal interference with daily activities	Causing greater than minimal interference with usual social and functional activities Interferes with normal everyday activity	Prevents performance of normal social and functional activities
Fatigue/malaise (decreased activity)	Easily tolerated	Interferes with normal everyday activity	Prevents normal everyday activity
Loss of appetite/anorexia	loss of appetite but no decrease in oral intake	Decreased oral intake but no weight loss	Decreased oral intake with weight loss or evidence of dehydration
Vomiting	Transient or intermittent AND no or minimal interference with oral intake	Frequent episodes with no or mild dehydration	Persistent vomiting resulting in need of aggressive rehydration (eg IV hydration)
Diarrhoea	Transient or intermittent episodes of unformed stools OR increase of ≤ 3 stools over normal in a 24-hr period	Persistent episodes of unformed or watery stools OR increase of 4-6 stools over normal in a 24-hr period	Increase of >7 stools a 24-hr period OR IV fluid replacement indicated
Nausea	Transient or intermittent AND no or minimal interference with oral intake	Persistent nausea with decrease in oral intake for 24 hrs	Persistent nausea with need for fluid replacement (eg, IV hydration)
Myalgia (muscle aches)	Muscle pain beyond the site of injection causing no or minimal interference with usual social and functional activities	Muscle pain beyond the site of injection causing greater than minimal interference with usual social and functional activities	Muscle pain causing inability to perform usual social and functional activities
Acute allergic reaction/urticaria	Localized without medical intervention	Localized with medical intervention OR mild angioedema without intervention	Generalized OR angioedema with intervention

Note: Grade 0 will be the classification if the observation is less than a Grade 1. Any grade 3 reactogenicity event that leads to an unscheduled visit to a healthcare provider will be recorded as an MAAE.

^a Temperature may be oral, tympanic, or noncontact (clinic only). Temperature greater than 40.0 °C (104.0 °F) is considered an SAE and subjects should seek medical attention immediately.

Source: Adapted from DAIDS Version 2.1, 2017.

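### The fever pause count matches the stated 3% only over all 360 subjects, not over Boostrix recipients, and fevers above 40.0 °C have no category in the severity tables

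*Protocol*

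**What the plan says.** Protocol Section 6.5 lists the events that halt enrolment and vaccination for Safety Monitoring Committee (SMC) review. The fever bullet reads "More than 12 subjects report a grade 3 fever within 7 days of study vaccination", requires attribution to vaccination with no other cause found, and adds in brackets "corresponding to an incidence rate of approximately 3% for Boostrix". It names no denominator, arm or stage of enrolment, and gives no source for the rate. Another bullet pauses the study for a single SAE considered related to vaccination.

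On numbers, Section 3.1 says "Approximately 360 subjects will be enrolled and randomly assigned (1:1:1) to 1 of 3 treatment groups". Table 3-1 and Section 5.2 give about 120 per group. Group A receives BPZE1 with an intramuscular placebo; groups B and C receive Boostrix.

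Table 1-1 (Section 1.3.1.3) is the protocol's own account of Boostrix fever rates. For ages 10 to 76, fever above 39.0 °C is in the Uncommon row, in the cell that continues "influenza like illness, pain". For ages 4 to 8, fever is in the Common row, which pools 37.5 °C and above with above 39.0 °C. The same section defines Uncommon as 0.1% to under 1% and Common as 1% to under 10%.

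Table 13-4 (Section 13.2), repeated as SAP Table 9-1-3, defines grade 3 fever as 39.0 to 40.0 °C and has no grade 4. Its footnote says that a higher temperature "is considered an SAE and subjects should seek medical attention immediately".

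**The concern.** The bracketed rate is the only justification given for the fever threshold, so a reader should be able to recover it. The percentage fits one denominator and the label fits another. If the SMC takes the text at face value, it may believe that the rule holds Boostrix recipients to about 3%, when 12 cases among them would be 5%.

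The count is also not tied to how many subjects have been vaccinated. The observed rate needed to reach it is therefore high early in the first BPZE1 study in school-age children and falls as enrolment proceeds.

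The closed upper end of the fever scale affects reporting. Solicited events through 7 days are the primary safety endpoint (SAP Section 3.2.1), and SAP Section 9.1 tabulates them by grade and by maximum severity on this scale. Read literally, a child with 38.6 °C on one day and 40.3 °C on another has grade 2 as the highest graded value. A temperature above 40.0 °C is also not literally a grade 3 fever for the count in 6.5, whereas the respiratory bullet in the same list covers grade 3 and anything higher.

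**Working it through.** **Inputs.** Threshold: more than 12 subjects, so the 13th triggers (Protocol 6.5). Subjects: about 360, of whom about 120 + 120 = 240 receive Boostrix (Table 3-1, Section 5.2). Lead-in cohort: 45 (Section 3.1). Dropout: 10% (Section 7.1). Substudy: up to 120 further vaccinations, BPZE1 only (Section 3.1.1).

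**Step 1: reproduce the stated rate.** 12/360 = 3.3%, and 13/360 = 3.6%. The stated figure reproduces on all enrolled subjects.

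**Step 2: try the other denominators.**

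| Denominator | n | 12/n | 13/n | 3% of n |
|---|---|---|---|---|
| All subjects | 360 | 3.3% | 3.6% | 10.8 |
| All, after 10% dropout | 324 | 3.7% | 4.0% | 9.7 |
| Boostrix recipients (B + C) | 240 | 5.0% | 5.4% | 7.2 |
| One arm | 120 | 10.0% | 10.8% | 3.6 |
| Vaccination occasions, full substudy | 480 | 2.5% | 2.7% | 14.4 |

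The 240 row supposes that all the counted fevers are in groups B and C; the rule itself counts every arm.

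**Step 3: read 3% as a background rate instead.** At ages 10 to 76, Table 1-1 puts fever above 39.0 °C below 1%, which excludes 3%. At ages 4 to 8 the 1% to under 10% band contains 3%, but it includes fevers from 37.5 °C upward and so does not give a rate for grade 3. Nine-year-olds are in neither column.

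**Step 4: how early the count can act.** The chance that the pause has been triggered by n vaccinated subjects is the exact binomial tail P(X ≥ 13 | n, p). The documents give no design rate, so p is an assumption: 3% is the stated rate, 6% is double it, and 10% is a large excess. A common rate across arms is assumed.

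| n vaccinated | Observed rate at 13th case | p = 3% | p = 6% | p = 10% |
|---|---|---|---|---|
| 45 | 28.9% | <0.01% | <0.01% | 0.03% |
| 120 | 10.8% | 0.01% | 2.8% | 42.4% |
| 180 | 7.2% | 0.3% | 28.6% | 92.0% |
| 240 | 5.4% | about 3% | 68.7% | 99.6% |
| 360 | 3.6% | 28.8% | 98.4% | >99.9% |

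If only one arm has a 10% rate and the other two have 1%, the chance is 2.7% by 60 per arm and 69.0% by 120 per arm.

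**Step 5: follow a temperature above 40.0 °C through the text.** It has no column in Table 13-4 or SAP Table 9-1-3. The footnote makes it an SAE. If judged related, it pauses the study at one case through the SAE bullet. It would appear in the SAE summaries and listings (SAP 9.2.4), and SAP 9.1 also summarises measured oral temperature in subjects with fever. It has no cell in the by-grade or maximum-severity tables.

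**The case against.** The strongest reply is that nothing is miscalculated: the rule counts subjects after any study vaccination, the study has 360 subjects, and 12 of 360 is about 3%. That stands. A reader might infer that the 3% is an arithmetic error, and the documents do not support this. The mismatch lies between the percentage and the words attached to it.

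A reader might also infer that Table 1-1 contradicts 3% for every child in the trial. It does so only for ages 10 and over. The younger column is compatible with 3%, and Section 1.3.1.3 refers to a product insert that is not reproduced, so a source may exist. What is missing is a statement of it.

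A third tempting inference is that the rule cannot act during most of enrolment. It can fire from the 13th case, and at a true 10% it has probably fired by mid-enrolment. Nor is it the only safeguard. Lead-in reactogenicity must be reviewed before the remaining subjects enrol, whatever the count; the medical monitor and medical lead may request SMC review at any time; and the related-SAE bullet needs only one case. Slow response near the threshold is a property of any fixed count and a design choice. These safeguards do not remove the need to state the denominator: the lead-in review covers only 45 subjects aged 11 to 17, and neither it nor the discretionary review has a stated fever criterion.

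Finally, it would be wrong to conclude that the highest fevers escape safety oversight. A related fever above 40.0 °C is treated more strictly than a grade 3 fever. What remains is the missing table category and the wording of the count.

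**Conclusion.** The point holds in two limited parts.

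First, the bracketed rate and its label do not share a denominator: 3.3% of all subjects against 5.0% of Boostrix recipients, or 5.4% at the trigger. As a background rate, 3% is unsupported by Table 1-1 at ages 10 to 76 and neither confirmed nor refuted at ages 4 to 8. This rests on the planned 120 per group. The early insensitivity is real (a 29% chance by 180 vaccinated at an assumed 6%), but it is context for reading the threshold and does not show that the threshold is wrong.

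Second, the fever scale is closed at 40.0 °C, so the by-grade and maximum-severity tables for a primary safety endpoint have no category for the highest temperatures. How many subjects this would affect cannot be estimated from the documents. The consequence is incomplete severity reporting and an unclear count in 6.5; a related event would still lead to a pause.

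**What to change.** 1. In Protocol 6.5, restate the rate with its denominator (12 is 3.3% of all 360 subjects and 5.0% of the roughly 240 Boostrix recipients). Say whether 3% is the rate implied by the count or a Boostrix background rate, give its source by age group, and reconcile it with Tables 3-1 and 1-1.
2. In the SAP by-grade and maximum-severity tables, add a reporting category for temperatures above 40.0 °C, so that a subject's highest reading determines where that subject is tabulated.
3. Reconcile the Table 13-4 footnote (and its copy in SAP Table 9-1-3) with the fever bullet, so that it is clear whether a temperature above 40.0 °C enters that count.

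The size of the threshold, and whether it should depend on the number vaccinated, remain for the sponsor and SMC; no value is proposed here. The cost is wording in one protocol section and one table footnote, plus an added category in the SAP tables. No new data are needed, because temperatures are already recorded in the diary.
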